12.6 Safety data

The safety analysis population will include all patients who received at least one dose of treatment and had a safety assessment performed at baseline. All safety parameters will be summarized and presented in tables based on this safety population.

Adverse event data will be presented in frequency tables (overall and by intensity) by System Organ Class and Preferred Term (MedDRA dictionary). In tables showing the overall incidence of adverse events, patients who experienced the same event on more than one occasion are counted only once in the calculation of the event frequency.

13.0 Monitoring

Monitoring visits to the study sites will be made by a qualified monitor to verify that the study is conducted according to study protocol, GCP principles and regulatory requirements. The monitor will verify the accurate and complete recording of data on CRFs, source documents and Investigators File.

The investigator/institution guarantees direct access to source documents of the study patients and to any other study related documentation. It is important that the investigator(s) and/or their relevant personnel are available during the monitoring visits.

14.0 DATA HANDLING AND RECORD KEEPING

14.1 Case Report Form (paper CRF)

Paper Case Report Form, provided by the Eudax, will be completed for each screened and enrolled subject. The language used must be English.

The completed original Case Report Forms are the sole property of SOFAR and should not be made available in any form to third parties, except for authorized representatives of appropriate regulatory authorities, without written permission from SOFAR.

The Investigator or an authorized staff member (medically qualified) has the responsibility to fill in, review and sign all Case Report Forms. However, the Investigator has final personal responsibility for the accuracy and authenticity of all data entered in the Case Report Form.

Subject source documents are the hospital subject records maintained at the study site. The investigator and Eudax must agree which items will be recorded in the source documents and for which items the patient's diary or the Case Report Form will stand as the source document. This must be stated in the "Data Location List" (to be archived in the Investigator File). One copy of this document should be returned to Eudax for filing into the Trial Master File.

14.2 Patient's diary

The patients will be provided with a diary at the Visit 1 and will be asked to report during the study period (Day 1-15)

information about:

- study drug compliance
- any other medications taken
- AEs
- Wound pain relief assessed using a 5-point Visual Rating Scale
- Pain intensity assessed using a 11-point Numerical Pain Rating Scale

The Investigator will instruct the subject about diary completion at the Visit 1 (Day 1), verify the completeness of the patient's diary at the Visit 2 (Day 8) and collect the completed patient's diary at Visit 3 (Day 15 -End of Study) after having checked the recorded information for completeness and accuracy.

If the information is complete and consistent, the Investigator can report a note in the hospital file referring to the diary and the diary itself will represent the source document for the data. If on the contrary the diary is incomplete or inconsistent, the Investigator should ask the patient for clarification and report in the subject records the correct information without making changes to the diary.

14.3 Data Handling

Data Management will be carried out by Eudax.

Medical terms are coded according to the MedDRA dictionary.

Previous and concomitant medications will be coded using the WHO-Drug Dictionary (WHO-DD).

Actual version of coding dictionaries will be notified in the final report.

The data are checked for completeness, accuracy and consistency by Eudax personnel. The errors detected will be rectified by means of Data Clarification Form/List (DCF/DCL) that will be used by the monitor for resolution of queries.

The original DCF/DCL must be archived together with the patient CRF.

The final data file will be transferred to SOFAR as soon as possible after the clinical investigation is completed.

14.4 Record Retention

To enable evaluation and/or audits and/or regulatory authority inspections, the Investigator agrees to keep the study related documents/records according to local regulations, but at least 7 years, or as specified in the Clinical Trial Agreement with SOFAR.

The documentation includes:

- the identity of all participating subjects ("Subject identification code list")
- all original signed informed consent forms
- copies of all case report forms
- source documents
- Investigator Study File

If the Investigator relocates, retires, or for any reason withdraws from the study, SOFAR should be notified in

advance and appropriate actions will be taken. The investigator must obtain SOFAR written permission before disposing of any records.

15.0 ETHICAL CONSIDERATION

15.1 Ethics Committee (EC)

Before initiating the study a written approval should be obtained by the EC for the study conduction.

Changes to the protocol can be made preparing written amendments to be agreed and signed by the Coordinating Investigator, SOFAR, Eudax and the Study Chairman. Before implementing any Protocol amendment, the EC written approval must be obtained. The only circumstance in which an amendment may be initiated prior to EC approval is where the change is necessary to eliminate apparent immediate hazards to the subjects. In that event, the EC must be notified in writing as soon as possible.

It is responsibility of Eudax to provide the Investigator with the EC approval (s). All the correspondence with the EC should be retained in the Investigator Study File.

15.2 Ethical conduct of the trial

The study will be performed in accordance with International Conference on Harmonization Good Clinical Practice guidelines, the Declaration of Helsinki and applicable local regulatory requirements.

15.3 Informed Consent

It is the responsibility of the investigator or delegate to give each patient (or the patient acceptable representative) full and adequate verbal and written information regarding the objective and procedures of the study and the possible risks involved. The patient must be informed about his/her right to withdraw from study at any time. The patient should have time and opportunity to enquire about the details of the study and to decide whether or not to participate. Written subject information must be approved by EC and must be obtained from each patient before any trial-related procedure is undertaken.

One copy of the signed and dated Informed Consent Form should be given to the patient. The originally signed document should be archived in the confidential section of the Investigator Study File.

The approved patient information sheet must not be changed without prior approval by SOFAR/Eudax and by the EC.

When new study information arise during the study, the patients still on treatment must be informed and a new Informed Consent form or an addendum to the already signed Informed Consent form must be signed and dated by the patients.

16.0 STUDY DISCONTINUATION CRITERIA

This study may be prematurely terminated or suspended, if in the opinion of SOFAR, Coordinating Investigator and the Study Chairman there is sufficient reasonable cause. Written notification documenting the reason for study

termination will be promptly provided to the investigators. Circumstances that may warrant termination include, but are not limited to:

- ✓ Determination of unexpected, significant, or unacceptable risk to patients
- ✓ Insufficient adherence to protocol requirements
- ✓ Insufficient complete and/or evaluable data

After such a decision, the investigator must promptly contact all participating patients to inform them about the decision taken.

Should the study be closed prematurely or suspended the EC should also be promptly informed and provided with the reason for termination or suspension.

17.0 INSURANCE

Not applicable.

18.0 CONFIDENTIALITY OF INFORMATION AND PUBLICATION OF RESULTS

All information supplied by Sofar/Eudax to the investigator is privileged and confidential information. The investigator agrees to use this information to accomplish the study and will not use it for other purposes without consent from SOFAR.

The investigator agrees to keep in confidence all the results obtained from the study. Such information shall not be disclosed to third parties without prior written permission from SOFAR/ except to regulatory authority(ies), when requested.

Individual investigators may present results of the study at scientific meetings. However prior to the submission, the SOFAR will have the opportunity to review and comment the abstracts for a period of up to 30 calendar days to allow SOFAR to assess properly that such proposed publication respects and/or is not in conflict with SOFAR's rights.

19.0 CLINICAL INVESTIGATION REPORT

A Clinical Investigation Report of the study will be prepared by the Eudax taking into consideration the ICH topic E3 (CPMP/ICH/137/95).

APPENDIX 1 - PAIN RELIEF EVALUATION

5-point Visual Rating Scale (VRS)

A Visual Rating Scale (VRS) is a measurement instrument that tries to measure a characteristic or attitude that is believed to range across a continuum of values and cannot easily be directly measured. For example, the amount of pain relief that a patient feels ranges across a continuum from none to complete. From the patient's perspective this spectrum appears continuous ± their pain relief does not take discrete jumps, as a categorization of none, slight, moderate, lots of, complete would suggest. It was to capture this idea of an underlying continuum that the VRS was devised.

Operationally a VRS is usually a horizontal line, 100 mm in length, anchored by word descriptors at each end, as illustrated below. The patient marks on the line the point that they feel represents their perception of their current state.

The VRS score is determined by measuring in millimetres from the left hand end of the line to the point that the patient marks.

How is your pain relief today? Place a vertical mark on the line below to indicate how you feel your pain relief today

0 1 2 3 4

No relief slight moderate lots of complete relief

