7.1 Duration of Clinical Investigation

After having signed the Informed Consent the patients will undergo a screening visit; patients fulfilling the inclusion/exclusion criteria will be enrolled in the study and treated once a day with ORTODERMINA® throughout a period of 14 days in addition to any therapy the physician will have prescribed for the treatment of the lesion.

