10.4.3 Wound examination

A wound examination will be carried out at the Visit 1, 2, 3.

10.4.4 5-point Visual Rating Scale (VRS) evaluations

Five-point VRS will be used by the patient to assess the pain relief over the treatment period. The patients mark on the scale their level of pain relief during the past 24 hours. This information is recorded by the investigator at the Visit 1, 2, 3 in the hospital record and by the patient daily in the diary.

10.4.5 11- point Numerical Pain Rating Scale evaluation

Eleven-point NPPS will be used by the patient to assess the pain intensity over the treatment period. This information is recorded by the investigator at the Visit 1, 2, 3 in the hospital record and by the patient daily in the diary.

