12.5 Efficacy Data

The primary analysis of efficacy will be based on the FAS population.

Efficacy will be evaluated according to an improvement in the pain relief (5-point Visual Rating Scale -VRS) and to the reduction of pain intensity (11-point Numerical Pain Rating Scale).

Wound pain relief from baseline (V1, Day 1) to end of treatment (V3, Day 15) will be analysed with a one-sample t-test, assuming a reference value equal to 0 (no relief) at baseline. Improvement in the pain relief will be observed with VRS scores at end of treatment significantly greater than 0.

Differences in pain Intensity from baseline (V1, Day 1) to end of treatment (V3, Day 15) will be analysed with a two-paired samples t-test. Improvement in the pain intensity will be observed with NPRS scores at end of treatment significantly lower than those at baseline.

All assessments coming from patient's pain daily diary concerning both relief and intensity will be reported descriptively and graphically.

Patients who will withdraw their consent before treatment start and who will fail to meet the inclusion criteria will be excluded from efficacy analysis.

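### The relief item names no comparison point, yet 12.5 analyses the Day 15 score as relief since Day 1 against an assumed baseline of 0

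*Combined protocol and SAP*

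**What the plan says.** **The item.** Appendix 1 asks about today's relief and instructs the patient: "Place a vertical mark on the line below to indicate how you feel your pain relief today". It explains the mark as follows: "The patient marks on the line the point that they feel represents their perception of their current state". The scale runs from 0 (no relief) to 4 (complete relief).

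**The protocol body.** Section 10.4.4 states the purpose: "Five-point VRS will be used by the patient to assess the pain relief over the treatment period". It then gives a recall window: "The patients mark on the scale their level of pain relief during the past 24 hours". On timing it says: "This information is recorded by the investigator at the Visit 1, 2, 3 in the hospital record and by the patient daily in the diary". The flow-chart also has the diary scales completed from Day 1 to Day 15. The Visit 1 list in 10.1 contains no relief rating; it ends with first administration and then diary distribution.

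**The analysis.** Section 12.5 describes the endpoint as relief from baseline (V1, Day 1) to end of treatment (V3, Day 15). It uses a one-sample t-test, "assuming a reference value equal to 0 (no relief) at baseline", and declares improvement if end-of-treatment scores are significantly above 0. The synopsis says the same. Section 12.2 makes the test one-sided and allows the pain-intensity test only if relief is significant.

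**Background therapy.** Under 7.1 the product is given "in addition to any therapy the physician will have prescribed for the treatment of the lesion". Section 9.4 prohibits only other compounds containing lidocaine.

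**The concern.** Relief is a comparative judgement. A score of 3 has no fixed meaning until the patient knows what today's pain is to be compared with. Section 12.5 needs the comparison to be with pain on Day 1 before treatment, and the item does not ask for that.

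Take a patient on stable wound or pain therapy whose pain is the same on Day 1 and Day 15. Compared with Day 1, the truthful answer is 0. Compared with untreated pain, it may well be above 0. The item permits both answers, and 12.5 reads the second as improvement since Day 1.

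Relief is the first primary endpoint and gates the second. The study has a single arm, so no control group absorbs relief that comes from other treatment. A score cannot fall below 0, so this error can only push the mean towards a positive result.

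**Working it through.** **1. The plan's own figure.** Inputs from 12.1: standardized effect 0.35, one-sided 5%, power 90%.

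n = ((1.645 + 1.282) / 0.35)² = 69.9, rounded up to 70. With 10% loss, 70 / 0.9 = 77.8, rounded up to 78. Both stated figures reproduce. (The exact t calculation gives 72, and 89.5% power at 70; the difference is immaterial here.)

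**2. The passages side by side.**

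| Place | Comparison point | Time window |
|---|---|---|
| Appendix 1, item | none | today / current state |
| 10.4.4 | none (purpose: over the treatment period) | past 24 hours |
| 12.5 | Day 1, set to 0 by assumption | Day 15 |

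The anchor that the analysis needs appears only in the analysis section. The two windows also differ.

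**3. How few patients are enough.** Assumption: nobody changes between Day 1 and Day 15, k of 70 patients mark 3 because of earlier therapy, and the rest mark 0.

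For k = 3:
- mean = 9/70 = 0.129
- variance = (27 − 70 × 0.1286²) / 69 = 0.3745, so SD = 0.612
- t = 0.1286 / (0.612 / √70) = 1.76 on 69 df, one-sided p = 0.042

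For k = 2, t = 1.43 and p = 0.079. So three patients are enough and two are not. The value of t is the same whether the three patients mark 1, 2, 3 or 4, because the scale factor cancels.

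**4. Range over the unknown share.** The documents give no share f of such patients. Under the same assumption, the chance of a significant result is P(K ≥ 3) with K ~ Binomial(70, f), and the standardized effect is √(f / (1 − f)).

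| f (assumed) | Chance of significance, no change since Day 1 | Standardized effect |
|---|---|---|
| 1% | 3% | 0.10 |
| 2% | 17% | 0.14 |
| 5% | 69% | 0.23 |
| 10% | 98% | 0.33 |

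At 10% the artefact is about as large as the design effect of 0.35.

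**5. Does the Day 1 score help?** A simulation (20,000 trials; assumed shares of 5% to 30% marking 3; assumed response noise of one point up or down, 15% each way, clipped to 0–4; no true change) tested Day 15 minus observed Day 1. It rejected in 4.8% to 5.0% of trials, close to the nominal 5%. Against a fixed 0 the same data rejected in about 100%.

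**6. What step 5 does not show.** The near-100% figure is not evidence for this point. With the same noise and no patient carrying earlier relief, 15% of patients still mark 1, because downward noise is clipped at 0. Then P(K ≥ 3) with K ~ Binomial(70, 0.15) is 99.9%. That result comes from placing the null at the floor of the scale.

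**The case against.** **The intent is visible.** Section 10.4.4 speaks of relief over the treatment period, and 14.2 has the investigator instruct patients on the diary. Section 12.2 defines its parameter as mean relief at the end of treatment, not as a change. This is fair, and it confines the conflict to 12.5 and the synopsis against the item. But the stated purpose is not in the item, a 24-hour window is not a comparison point, and no passage says what the instruction should contain. The working diary page is not among the documents, so an anchor given there cannot be excluded.

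**Pain intensity is unaffected.** It is paired with its own Day 1 value, so its estimate stands. It is tested only after relief succeeds, however.

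A reader might also infer more than the documents support:

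- *That the error cannot be removed in the analysis.* For stable relief from earlier therapy it can, because 10.4.4 and the flow-chart provide a Day 1 score. Only other reference points, such as yesterday, would resist correction, and nothing shows that patients would use them.
- *That the Day 1 rating is pre-treatment and meaningless, and should go.* No passage says it precedes the first application. Section 10.1 lists administration before diary distribution, and the SmPC gives onset in 3–5 minutes. It is also the only data that could test the assumed zero.
- *That the bias has a known size.* Any share of patients using a different reference would be assumed.
- *That the very high rejection rates stem from the wording.* Most of that is the floor effect in step 6.

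**Conclusion.** The concern holds in this form: item and analysis do not refer to the same comparison, and with background therapy continuing, the plan as written can count relief already present on Day 1 as improvement since Day 1. This affects the gating primary endpoint.

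The size is unknown. The calculations show sensitivity only: three of 70 patients can be enough, if all others mark 0 and nobody changes. The chance of a false positive result then runs from 3% to 98% as the assumed share goes from 1% to 10%.

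The change should be made. The sample size is not in question: 70 evaluable and 78 enrolled stand if the effect of 0.35 is kept.

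**What to change.** 1. Reword the item with one anchor and one window, keeping the 0–4 labels, for example: *Compared with your wound pain before you first applied ORTODERMINA on Day 1, how much pain relief have you had during the past 24 hours?*
2. Align Appendix 1, 10.4.4, 12.5 and the synopsis with that wording.
3. Keep the Day 1 relief rating. State whether it is taken before the first application, reconcile 10.1 (no rating listed) with 10.4.4 and the flow-chart, and use the rating to check the assumed zero.
4. If the present wording stays, test Day 15 minus the observed Day 1 score instead of Day 15 against a fixed 0. This removes stable earlier relief only if the Day 1 rating precedes the first application, and it cannot recover which reference each patient used.

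**Cost.** One sentence on the diary page and matching edits in the sections named. The downside is that patients must recall Day 1 pain over 14 days.

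**Not cured.** Rewording leaves the null at the floor of a non-negative scale, where a few positive marks can reject it. That needs separate treatment.

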APPENDIX 2 - PAIN INTENSITY EVALUATION

11-point Numerical Pain Rating Scale (NPRS)

Select the number that best describes your pain during the past 24 hours (*circle only one number*):

0	1	2	3	4	5	6	7	8	9	10
No Pain										Worst possible Pain

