5.0 STUDY OBJECTIVES

5.1 Primary Objectives

- To observe wound pain relief in patients with painful wounds treated with ORTODERMINA®

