6.0 STUDY END-POINTS

6.1 Primary End-points

- Wound pain relief based on using a 5-points Visual Rating Scale (14) (Appendix 1)
- Pain intensity based on a 11-point Numerical Pain Rating Scale (15) (Appendix 2)

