9.4 Concomitant Medication

Other compounds containing Lidocaine will not be allowed for the entire study period. Patient using other compound containing Lidocaine during the study will be excluded from the efficacy analysis.

Any additional treatment/medication including any compound prescribed for the routine treatment of the target lesion, taken by the patient during study period, started before the patient's enrolment in the study (ongoing treatment) or started during the patient's participation in the study will be report in the CRF. The patient will be required to record in the diary any new medication used during the study period (Day 1-14).

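### Neither patient pain item names the wound, and the target lesion is never defined, so pain from other sources can enter both primary endpoints

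*Combined protocol and SAP*

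**What the plan says.** Section 5.1 states the primary objective as "To observe wound pain relief in patients with painful wounds treated with ORTODERMINA". Section 6.1 lists two primary endpoints: "Wound pain relief based on using a 5-points Visual Rating Scale" and "Pain intensity based on a 11-point Numerical Pain Rating Scale". The first names the wound; the second does not.

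The printed relief item in Appendix 1 reads "How is your pain relief today". The printed intensity item in Appendix 2 reads "Select the number that best describes your pain during the past 24 hours". Section 10.4.4 describes the relief rating as "The patients mark on the scale their level of pain relief during the past 24 hours". Section 10.4.5 describes the intensity rating in similarly general terms. Neither section refers to a wound.

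Section 9.4 mentions compounds prescribed for the "routine treatment of the target lesion", and sections 10.1 to 10.3 repeat the term when listing concomitant medication. No section says how that lesion is chosen, where it is recorded, or that the pain ratings refer to it. Section 10.4.3 schedules a wound examination at all three visits without naming an index wound. Eligibility (section 8.2) speaks of wounds in the plural and does not exclude patients with other painful conditions.

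Section 14.2 labels the relief scale in the diary as wound pain relief and the other scale simply as pain intensity. It has the investigator instruct the patient on completing the diary at Visit 1 and check the entries at Visits 2 and 3. It does not say what the instruction contains.

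**The concern.** The objective is about wound pain, but the instruments ask about the patient's pain or pain relief in general. A patient who also has joint or back pain and answers the printed question as written reports a mixture of the two. Both primary tests in section 12.5 use these ratings directly: relief at Day 15 against 0, and intensity at Day 1 against Day 15.

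The error can go either way. Pain elsewhere that does not change dilutes the before-after difference. Pain elsewhere that improves adds a change that would be credited to the product. The study has one arm (section 7), so no comparator would show either effect. The plan does not record which pain a rating refers to, so analysts cannot separate the sources afterwards.

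**Working it through.** **Text comparison**

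| Place | Refers to the wound? |
|---|---|
| Primary objective, 5.1 | Yes |
| Endpoint 1 (relief), 6.1 | Yes |
| Endpoint 2 (intensity), 6.1 | No |
| Relief assessment, 10.4.4 | No |
| Intensity assessment, 10.4.5 | No |
| Relief item, Appendix 1 | No |
| Intensity item, Appendix 2 | No |
| Diary label for relief, 14.2 | Yes |
| Diary label for intensity, 14.2 | No |
| Target lesion, 9.4 and 10.1–10.3 | Named for concomitant medication only; not defined |

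The direct mismatch is on the relief scale, where the endpoint says wound and the item does not. For intensity, the item agrees with its endpoint label, and the mismatch is with the objective in 5.1.

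**The plan's own sample size**

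Inputs from section 12.1: standardized effect 0.35, one-sided 5%, power 90%.

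- Normal approximation: n = ((1.645 + 1.282)/0.35)² = 69.9, rounded up to 70.
- With 10% inflation: 70/0.9 = 77.8, rounded up to 78.
- Exact power of the one-sided t-test at n = 70 (noncentral t, 69 degrees of freedom, noncentrality 0.35 × √70 = 2.93): 89.5%.

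The figures 70 and 78 reproduce and are not in dispute.

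**Illustration of dilution**

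The documents give no share of patients with other dominant pain, so a share f of 20% or 30% is assumed. Those patients' ratings have mean change 0. The others have mean change 0.35 in units of their own SD (set to 1). The overall mean is 0.35 × (1 − f): 0.28 at 20% and 0.245 at 30%. The result then depends on how variable the f group's ratings are.

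1. Overall SD held at 1. The standardized effects are 0.28 and 0.245.
2. The f group varies as much as the others, and the difference in means between the groups is added. Variance = 1 + f(1 − f) × 0.35², which is 1.0196 and 1.0257. The effects are 0.28/1.0098 = 0.277 and 0.245/1.0128 = 0.242.
3. The f group shows exactly zero change, with no variability. Variance = (1 − f) + f(1 − f) × 0.35², which is 0.8196 and 0.7257. The effects are 0.28/0.9053 = 0.309 and 0.245/0.8519 = 0.288.

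Exact one-sided 5% t-test power at n = 70:

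| Variance assumption | f = 0 | f = 20% | f = 30% |
|---|---|---|---|
| 1. SD held fixed | 89.5% | 75.0% | 65.0% |
| 2. Mixture, equal variability | 89.5% | 74.3% | 64.0% |
| 3. Mixture, zero variability in the f group | 89.5% | 82.1% | 77.0% |

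Assumptions 1 and 2 nearly coincide, so the range is about 75–82% at 20% and 65–77% at 30%.

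**Which endpoint this applies to**

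It applies mainly to the intensity scale. Section 12.5 tests relief against 0 on a scale whose lowest value is 0, so dilution is unlikely to prevent rejection there. For relief, the effect is on what the mean score represents.

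**The case against.** - **One wound, no other pain.** For such a patient the general question and the wound question coincide. This stands. A reader might infer that the ratings fail to measure wound pain at all, but the documents do not support that. Ratings may be contaminated in patients with other pain; they are not invalid as a whole.
- **Several wounds.** The objective and eligibility are in the plural. Nothing limits treatment to one wound, and the product information in Appendix 4 speaks of the affected area. If all wounds are treated, a rating that covers all of them fits the objective. This stands too. One might infer that a single index wound is required, or that a patient's other wounds go untreated; the documents say neither. What is missing is a record of which wounds are meant.
- **The diary.** It is not in the documents and may carry wound-specific wording. Section 14.2 labels relief as wound pain relief and provides for instruction and checking. This is partial mitigation. The content of the instruction is not stated, the intensity label names no wound, and the appendices print the items without one.
- **The power figures.** The 20% and 30% shares are assumed, and the loss is smaller if the affected patients show no variability. Both points are correct, and the result is therefore given as a range.
- **Systemic analgesics.** These would also lower pain in the treated wound, so rewording does not remove their effect. This is correct. Other lesion therapy is allowed (section 7.1), and section 9.4 prohibits only other lidocaine products.

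**Conclusion.** The point holds as a gap in the measurement of both primary endpoints. The objective and first endpoint are wound-specific, the printed items are not, and the target lesion is neither defined nor tied to the ratings. In patients with other pain, the ratings may be contaminated in either direction, and the single-arm before-after design offers no way to detect it.

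The size cannot be fixed from the documents. Under the assumed shares, power for the intensity comparison falls from 89.5% to about 75–82% (20% of patients) or 65–77% (30%). This rests on unchanged pain elsewhere and an effect of 0.35 in the remaining patients. It does not show that the planned 70 evaluable patients is wrong. The change should be made because the ambiguity affects the primary data, cannot be repaired in analysis, and is cheap to remove.

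**What to change.** 1. Reword the items in Appendices 1 and 2 so that they ask about pain relief and pain in the wound or wounds treated with the study product, over the past 24 hours. For the relief item this also replaces the reference to today with the recall period in section 10.4.4.
2. Use the same wording in sections 10.4.4 and 10.4.5 and in both diary labels in section 14.2.
3. Define the target lesion. Record at Visit 1 which wound or wounds it comprises, and examine the same ones at Visits 2 and 3.

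The cost is a few words on the form and one CRF field, with no extra visit. If ratings have already been collected on the printed items, the report should say that the items did not name the wound. Bias from permitted systemic analgesics remains and should be stated as a limit of the single-arm design.
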